13.4.2 Immune-Related Response

Tumor response to nivolumab based on immune-related response criteria (IRC) will also be assessed. Responses will be summarized descriptively using frequencies and percentages. See section 11 for details on IRC response.

13.4.3 Duration of Response

Defined for all evaluable patients who have achieved an objective response as the date at which the patient's objective status is first noted to be either a CR or PR to the date progression is documented for both response criteria (RECIST 1.1 and IRC).

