5.7 Treatment Beyond Progression

A minority of subjects treated with immunotherapy may derive clinical benefit either delayed responses, stable disease, or increased overall survival despite initial evidence of progressive disease (PD) with nivolumab or combination treatment.

Patients may be permitted to continue treatment beyond initial RECIST 1.1-defined PD occurring during the initial induction period (up to 12 weeks), as long as they meet all of the following criteria (see section 5.7.1 below). Patients are allowed to continue treatment for one additional cycle (4 weeks) and then be reassessed.

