5.7.1 Criteria for Continuing Treatment Beyond Progression

- 1) No more than 4 new lesions (excluding new brain metastases), with the total sum of the longest diameter (SHORT diameter for LN) cannot exceed 40% of the initial sum including new lesions
- 2) Patients must be clinically stable with no change in performance status due to disease progression
- 3) No indication for immediate alternative treatment (such as radiotherapy).
- 4) Patient [assessed by the investigator] is showing clinical benefit and tolerates study drug. The assessment of clinical benefit should take into account whether the subject is clinically stable or deteriorating and likely or unlikely to receive further benefit from continued treatment.
- 5) The time of progression is noted from the first assessment that exceeds standard criteria

New lesions are considered measurable at the time of initial progression if the longest diameter is at least 10 mm (except for pathological lymph nodes, which must have a short axis of at least 15 mm). Any new lesion considered non-measurable at the time of initial progression may become measurable and therefore included in the tumor burden measurement if the longest diameter increases to at least 10 mm (except for pathological lymph nodes, which must have an increase in short axis to at least 15 mm).

All decisions to continue treatment beyond initial progression must be documented in the study record and are a part of an agreement with DCTD, NCI.

For statistical analyses: Subjects who continue treatment beyond first progression (as determined by the initial investigator-assessed, RECIST 1.1-defined progression) will be considered to have investigator-assessed ‘progressive disease’ at the time of the initial

progression event. However, if they subsequently experience a CR or PR they may be designated as a ‘delayed response’ for the purposes of determining ORR and thus, in the final analysis, be counted as a responder for the two-stage design.

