13.1.2 Primary Endpoint

The primary endpoint of this trial is the confirmed response rate using RECIST 1.1 criteria. All patients meeting the eligibility criteria who have signed a consent form and have begun treatment will be considered evaluable for the primary endpoint. A confirmed tumor response is defined to be a CR or PR noted as the objective status on 2 consecutive evaluations at least 4 weeks apart (within 8 weeks and not less than 4 weeks apart).

- For late responders to nivolumab (see section 5.7.1): Subjects who continue treatment beyond first progression (as determined by the initial investigator-assessed, RECIST 1.1-defined progression) will be considered to have investigator-assessed ‘progressive disease’ at the time of the initial progression event. However, if they subsequently experience a CR or PR, they may be designated as a ‘delayed responder’ for the purposes of determining ORR and thus, in the final analysis, be counted as a ‘responder’ for the study.

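### RECIST 1.1 duration of response conflicts with the delayed-responder rule: progression is dated before the response that starts the clock, and no later end point is defined

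*Combined protocol and SAP*

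**What the plan says.** Duration of response is a secondary objective (section 1.2.2). Section 13.4.3 gives its population as "Defined for all evaluable patients who have achieved an objective response", with no exclusion of delayed responders. The interval runs from the date the status is "first noted to be either a CR or PR to the date progression is documented". The same definition is applied under RECIST 1.1 and under IRC.

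Section 13.1.2 deals with patients treated past a first RECIST 1.1 progression. They keep that first progression as their progression date. A later CR or PR can nevertheless make such a patient a delayed responder and so a success in the final response count; the designation is permissive ("However, if they subsequently experience a CR or PR, they may be designated as a"). Section 5.7.1 carries a near-identical statement for the statistical analyses, and its item 5 adds: "The time of progression is noted from the first assessment that exceeds standard criteria".

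Section 5.7 limits the initial PD to the first 12 weeks and allows one further 4-week cycle before reassessment. Section 11.1 schedules scans at weeks 8, 16 and 24, then every 12 weeks.

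**The concern.** A delayed responder is, by definition, someone whose CR or PR comes after the initial PD. Sections 5.7.1 and 13.1.2 date the progression at that PD; section 13.4.3 starts the clock at the CR or PR and stops it at progression. Taken together, the stop comes before the start.

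The analyst would then have to choose, possibly with the results in view, between entering a negative or zero value, dropping the patient, or timing the response to a later progression. Dropping the patient would leave the response rate and its duration describing different sets of responders. Durability is also part of the argument for the drug. Section 13.1.1 contrasts long-lasting nivolumab responses with short-lived responses to cytotoxic agents, and section 13.1.7 lists duration of response among the matters weighed in any decision to terminate the study.

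**Working it through.** The plan states no figure for duration, so there is none to reproduce. The check is date arithmetic, followed by a comparison of the rules.

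**Step 1: the literal interval.** Duration = date of documented progression (13.4.3, fixed at the initial PD by 5.7.1 and 13.1.2) minus date of first CR or PR (13.4.3). The only scheduled scan inside the 12-week window is week 8. Week 12 is the reassessment after one more cycle; weeks 16 and 24 are scheduled scans.

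- PD week 8, CR or PR week 12: 8 - 12 = -4 weeks
- PD week 8, CR or PR week 16: 8 - 16 = -8 weeks
- PD week 8, CR or PR week 24: 8 - 24 = -16 weeks
- PD week 12 (unscheduled scan), CR or PR week 16: 12 - 16 = -4 weeks

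The sign is negative whenever the first CR or PR follows the PD. A patient with a CR or PR before the initial PD would have a positive interval, but with the first scan at week 8 and the PD limited to 12 weeks that group is nearly empty.

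**Step 2: is a later progression defined?** Two cases differ.

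- *Initial PD from growth of target lesions.* Section 11.4.3 defines progression as a rise of at least 20% and 0.5 cm over the minimum sum of section 11.4.1. That can be borrowed for regrowth after the response, although no section says that progression is re-opened after the initial PD.
- *Initial PD from new lesions.* Section 5.7.1 allows up to 4 of them. The table in section 11.44 returns PD whenever new sites are recorded, whatever the target lesions do. While those lesions persist, the table marks no distinct later progression.

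**Step 3: what else is touched?**

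- *IRC duration.* Section 11.5 adds measurable new lesions to the total burden and requires a rise of at least 25% over nadir on two consecutive observations. A RECIST 1.1 PD followed by shrinkage need not be an IRC progression, so the IRC interval will often be an ordinary positive one.
- *PFS (13.4.4).* It ends at the first progression or death, which is the initial PD. There is no conflict.
- *Decision rule (13.1.4).* It counts confirmed responses and does not use duration.

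**Step 4: how far the choice could matter (invented data).** Take 35 x 0.20 = 7 responders with assumed durations of 16, 20, 28, 36, 44, 52 and 64 weeks, all ending in observed progression. Let the longest belong to one delayed responder. The median is then:

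- entered as -8: values -8, 16, 20, 28, 36, 44, 52; median 28 weeks
- dropped: values 16, 20, 28, 36, 44, 52; median (28 + 36)/2 = 32 weeks
- timed to a second progression: all seven values; median 36 weeks

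This shows only that the choice can move the result. It is not an estimate of the effect in this trial.

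**The case against.** The strongest reply is that the negative value comes from one literal reading. Section 13.4.3 does not say first progression, whereas the PFS definition in 13.4.4 does take the first event. A clock that starts at a response is naturally stopped by a progression after it, and neither 5.7.1 nor 13.1.2 mentions duration. Section 11 already defines progression against a running minimum, so only a linking sentence would be missing.

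Part of this stands. The next progression is the sensible reading, and the section 11 rule would serve for target regrowth. But sections 5.7.1 and 13.1.2 fix the progression for statistical purposes, nothing re-opens it, and the section 11.44 table gives no usable later event while new lesions persist. The rules as stated conflict.

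Other limits stand in full. The endpoint is secondary and has no stated test. Section 5.7 speaks of a minority who may benefit in any of several ways, section 5.7.1 adds conditions, and the responder designation is permissive.

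A reader might infer more than the documents support:

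- *That such patients cannot be placed on a duration curve.* Section 13.4.3 specifies no curve; Kaplan-Meier is named only for PFS and OS.
- *That one delayed responder among the 7 expected (1/7 = 14%), or among the 4 needed for success (1/4 = 25%), measures the damage.* These are shares of responders, not changes in estimated duration, and the 4 belongs to a decision rule that the issue does not touch.

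**Conclusion.** The point holds for the RECIST 1.1 duration of response. Read literally, the plan gives a negative interval for every delayed responder whose first CR or PR follows the initial PD, for example -4 or -8 weeks. Read more generously, it does not say which later progression ends the response.

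A broader conclusion, that the plan's duration results as a whole or its main efficacy conclusions are unsound, is not supported: the IRC duration is largely unaffected, and PFS and the primary decision rule are untouched. The effect on the reported duration cannot be sized from the documents because the number of delayed responders is not given and may be zero. The week-12 and week-16 examples assume PD at the first scheduled scan and a response at the next reassessment or scheduled scan. The correction should be made before the analysis, but nothing in the design depends on it.

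**What to change.** Add to section 13.4.3:

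> For a delayed responder, RECIST 1.1 duration runs from the first CR/PR after the initial PD to the first later progression by the section 11 criteria, judged against the smallest sum recorded from the initial PD onward; measurable lesions that were new at the initial PD are included in that sum and do not by themselves count again as new disease. The initial PD remains the PFS event.

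Starting the reference sum at the initial PD is a deliberate departure from the running minimum in section 11.4.1, because from that date the sum also contains the new lesions. Section 5.7.1 already states when a new lesion is measurable and can be cross-referenced.

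Showing duration with and without delayed responders is optional. The cost is a wording change and slightly more analysis work; no treatment rule or scan changes.

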13.4.4 Progression-Free Survival (PFS)

Defined as the time from registration to the first of either death due to any cause or progression. The distribution of PFS will be estimated using the method of Kaplan-Meier [46].

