4.4 Screening and General Guidelines

Following registration, patients should begin protocol treatment \leq 21 days. Issues that would cause treatment delays should be discussed with the Principal Investigator. If a patient does not receive protocol therapy following registration, the patient's registration on the study may be canceled. The Study Coordinator should be notified of cancellations as soon as possible. After the consent form is signed, refer to section 10 'Study Calendar' for screening procedures. Standard contrast CT will be done for assessing non-local recurrences. MRI will be used for assessing local recurrence. If dual PET and contrast CT is used to assess non-local recurrences at baseline, all subsequent radiological assessments must include a PET-CT.

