11.1 Schedule of Evaluations

For the purposes of this study, patients should be re-evaluated for objective tumor response at week 8 after the first dose of nivolumab, and then at week 16 and week 24, and then every 12 weeks thereafter. In addition to a baseline scan, confirmatory scans should also be obtained within 8 weeks (not less than 4) following initial documentation of objective response.

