Therefore, we have decided to use the data from two of our prior phase II studies of targeted agents, namely, pazopanib and cetuximab (the latter in combination with carboplatin) for calculating the sample size in this proposal because the cohort in these studies are similar to the current proposal. In the pazopanib study, patients had a median of 3 lines of therapy, and clinical benefit rate (CBR, PR + SD + CR) at 12 weeks was used to calculate the sample size. A CBR of 35% was estimated to be clinically meaningful, and the actual rate reported was > 50% [39]. The ORR was 6.1%, median TTP was 4.4 months (95% CI: 3.9–5.8 months) and the PFS-6 month was around 30-35% (read from the curve). In the cetuximab study [40], 70% of patients had 1 prior line of chemotherapy only. Although the ORR was 11.7% and the CBR rate was 60% (which is higher than the pazopanib study), the median TTP was quite short at 2.7 months, and the PFS-6 months was around 20-30% (read off the curve) [40]. Therefore, the average PFS at 24 weeks (6 months) is around 25-30% a benchmark for heavily-pretreated NPC patients, with a ORR between 6% to 20%.

These prior studies have shown that the response rate is generally around 5% in this disease setting [39-40]. If Nivolumab can increase the response rate to 20% or more, that would be exciting and worth further study. This protocol will assess the confirmed response rate as the primary endpoint. In addition this study will assess multiple secondary endpoints, including adverse events, tumor response to nivolumab based on immune-related response criteria (IRC), duration of response, progression-free survival (PFS), overall survival (OS), and laboratory correlates.

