13.4 Analysis of Secondary Endpoints

This study will assess multiple secondary endpoints, including adverse events, tumor response to nivolumab based on immune-related response criteria (IRC), duration of response, progression-free survival (PFS), overall survival (OS), and laboratory correlates. The analysis population for these endpoints will be the same as that for the primary endpoint – i.e., all patients meeting the eligibility criteria who have signed a consent form and have begun treatment.

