13.4.5 Overall Survival

Defined as the time from registration to death due to any cause. The distribution of survival time will be estimated using the method of Kaplan-Meier [46]. Special attention will be paid to any registered patient who dies early (i.e., within 60 days) of initiating their treatment. Circumstances surrounding such early deaths will be classified as being either due to malignant disease, toxicity, other causes, or of unknown reasons.

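### PFS and OS are timed from registration but analysed only in patients who later started treatment, so both are modestly biased upward in absolute terms

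*Combined protocol and SAP*

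**What the plan says.** Section 13.4.4 gives the PFS definition: "Defined as the time from registration to the first of either death due to any cause or progression". Section 13.4.5 does the same for OS: "Defined as the time from registration to death due to any cause". Both are to be estimated by Kaplan-Meier; neither section names a landmark, a null value or a test.

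Section 13.4 sets the population for these endpoints: "all patients meeting the eligibility criteria who have signed a consent form and have begun treatment".

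The two starting points can differ. Section 4.4 reads "Following registration, patients should begin protocol treatment" and gives a limit of 21 days, worded as an expectation, with longer delays to be discussed with the Principal Investigator. It adds: "If a patient does not receive protocol therapy following registration, the patient's registration on the study may be canceled".

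The imaging clock starts at dosing. Section 11.1 states that "patients should be re-evaluated for objective tumor response at week 8 after the first dose of nivolumab", then at weeks 16 and 24, then every 12 weeks. Section 10 ties the baseline scan to the start of therapy and allows ±7 days for imaging from week 16.

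Section 13.1.1 gives outside context: "the average PFS at 24 weeks (6 months) is around 25-30% a benchmark for heavily-pretreated NPC patients". The decision rule in 13.1.4 uses confirmed response only.

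**The concern.** Whether a patient enters the analysis set is decided by an event, the first dose, that comes after the PFS and OS clock has started. A patient in the set must have been alive at first dose, so the interval from registration to dose is immortal time for OS. For PFS the same holds for death, and no response assessment falls in that interval. Patients who die or worsen before dosing leave the numerator and the denominator together. Both features act in one direction: they lengthen PFS and OS.

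The scan schedule adds a second effect. A progression found at the week-24 scan is dated about 24 weeks after first dose, and therefore later than that after registration. Even a short gap can push many of these events past a 24-week reading.

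With a single arm, there is no concurrent control in which the bias would cancel. The same PFS and OS times also feed the Kaplan-Meier and Cox analyses of biomarkers in 13.4.6.

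**Working it through.** **Inputs from the documents.** Gap from registration to first dose: up to 21 days (4.4). Scans at weeks 8, 16 and 24 from first dose (11.1), with ±2 days for visits and ±7 days for imaging from week 16 (section 10). Evaluable patients: 35; maximum accrual: 40 (13.2.1). Benchmark 24-week PFS: 25-30% (13.1.1).

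**The plan's own figure.** The two source studies in 13.1.1 have 6-month PFS of 30-35% and 20-30%, both read from curves. Averaging the ends gives (30 + 20)/2 = 25% and (35 + 30)/2 = 32.5%. The lower end matches the stated range; the upper end is 2.5 points higher, which is unremarkable for values read off a graph. No sample size, error rate or decision depends on this figure. It is used below only to fix a plausible PFS level.

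**Step 1: shift in the median.** If every patient waits g before dosing and the set contains only dosed patients, the whole curve moves right by g. At the full 21 days, g = 21/30.44 = 0.69 months. With exponential PFS and a 24-week rate of 27.5%, the median is 24 × ln(0.5)/ln(0.275) = 12.9 weeks from first dose and 15.9 weeks from registration.

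**Step 2: shift at 24 weeks, continuous time.** If S is the 24-week rate from first dose, the rate read at 24 weeks from registration is S^((24 − g)/24), with g in weeks.

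| S from first dose | g = 1 week | g = 2 weeks | g = 3 weeks |
|---|---|---|---|
| 25% | 26.5% (+1.5) | 28.1% (+3.1) | 29.7% (+4.7) |
| 27.5% | 29.0% (+1.5) | 30.6% (+3.1) | 32.3% (+4.8) |
| 30% | 31.5% (+1.5) | 33.2% (+3.2) | 34.9% (+4.9) |

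**Step 3: progression found at scans.** This was simulated with a latent 24-week rate of 27.5% and the scan windows above. The share of events that fall off schedule (deaths, symptomatic deterioration) is an assumption.

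- With 10% off schedule, 24-week PFS is about 34.5% from first dose. From registration it is about 38% for a gap of half a week, 40% for gaps uniform over 0-3 weeks and 41% if all gaps are 3 weeks. The origin adds about 3, 5.5 and 7 points respectively.
- Once the gap reaches 1 week, even an early week-24 scan falls at or beyond 24 weeks from registration, so a longer gap adds little more.
- With the off-schedule share varied from 0 to 50% and gaps uniform over 0-1 to 0-3 weeks, the origin adds about 2 to 6 points.

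Across these settings the origin effect is roughly 2 to 7 points. The rise from 27.5% to about 34.5% comes from scan timing and is present with a first-dose clock too, so it is not part of this point.

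**Step 4: OS.** There is no scan component. Assuming an exponential median OS of 9 to 15 months, the chance of death within 21 days is 1 − exp(−ln 2 × 0.69/median) = 5.2% to 3.1%, or about 1 to 2 of 40 patients. The median moves by at most 0.69 months.

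**Step 5: sampling error.** At n = 35 and 27.5%, the 95% half-width is 1.96 × √(0.275 × 0.725/35) = 14.8 points.

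**The case against.** The strongest reply is that nothing in the plan is decided on PFS or OS. Sections 13.4.4 and 13.4.5 call for Kaplan-Meier estimates, and the trial succeeds or fails on confirmed response. That stands, and it limits the importance of the point.

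The 21 days is an intended ceiling, not a typical value. Eligibility is verified before enrolment (4.3.2), and baseline bloods are due within a week of starting therapy (section 10). Unless those bloods are repeated, this suggests shorter gaps. That also stands: the actual gaps are unknown, so the larger figures are upper readings.

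A reader might infer that PFS is inflated against the 25-30% figure in 13.1.1. The documents do not support that. They give no time origin, analysis set or scan schedule for the two source studies. If those studies also timed from registration in treated patients, the bias could cancel in the comparison. The plan specifies no formal comparison either.

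A reader might also see a contradiction in 13.4.5, which reviews early deaths within 60 days of starting treatment while timing OS from registration. That review concerns causes of early death and is naturally tied to treatment; it is not a second OS definition.

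Finally, section 4.4 says an untreated patient's registration may be cancelled, not that it will be. The exclusion comes from the population in 13.4, and it probably concerns few patients: the 5 extra places in 13.2.1 cover ineligibility, cancellation, major violations and other reasons together.

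None of this removes the mismatch between the clock and the analysis set, or its direction.

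**Conclusion.** The point holds as a definitional mismatch with a known direction and modest size. Followed as written, the plan overstates absolute PFS and OS in the treated patients. At 24 weeks the origin adds about 1.5 to 4.8 points in continuous time and roughly 2 to 7 points with scan-detected progression. Medians lengthen by the gap, at most 0.69 months if the 21-day limit is kept.

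These sizes assume exponential PFS with a 24-week rate of 27.5%, gaps of up to 3 weeks, and an assumed share of off-schedule events. The bias is smaller than the ±15 points of sampling error, but more patients would not remove it. It does not affect the primary endpoint, the sample size or the go/no-go rule. Whether it distorts a comparison with the 25-30% figure cannot be determined from the documents.

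It is tempting to deal with scan timing by reading this trial's curve a week later, at the end of the scan window. That would set unequal time points against outside figures whose own scan windows are unknown, and it could bias against the drug.

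**What to change.** In 13.4.4 and 13.4.5, count PFS and OS from the first nivolumab dose and keep the treated population of 13.4. This puts the endpoint clock, the scan clock and entry to the analysis set on the same day. It is a wording change using dates the trial needs anyway; reported PFS and OS become slightly shorter, and the results then describe treated patients only.

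The alternative is to keep registration as the origin and include all eligible registered patients, treated or not. That removes the selection but costs more. Patients who never start must be followed rather than cancelled, a censoring rule is needed for those never scanned, and the offset between the scan clock and the PFS clock remains.

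With either choice, reporting the distribution of days from registration to first dose would let readers judge the size of the effect.
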